## 1. AMENDMENT HISTORY

Amendment No.	Protocol Version No.	Date issued	Author(s) of changes	Details of Changes made

## 2. SYNOPSIS

The study will compare the pressure distribution between novel proning pillows and standard pillows used in the ICU. NHS staff will be recruited and will be asked to lie on each pillow for a short period of time. The pressure distribution will be measured using a pressure mat placed between the subject and pillow.

Study Title	Proning pillows for Intensive Care Unit (ICU): Comparison of chest and pelvis interface pressure distributions between a novel proning pillow system and standard pillows in healthy subjects
Internal ref. no.	SP0857
Type of study	Interventional
Trial Design	Cross-sectional comparative study
Trial Participants	NHS staff
Planned Sample Size	50
Follow-up duration	N/A
Planned Trial Period	1 year
Primary Objective	To evaluate any differences in chest and pelvis interface pressures between novel proning pillows and standard pillows used in ICU.
Secondary Objectives	N/A
Primary Endpoint	Peak interface pressure differences between the two pillows
Secondary Endpoints	N/A
Device Name	Prone Pillow System
Manufacturer Name	Putnam Health Co Ltd (Devon, UK)
Principle intended use	The proning system has been specifically designed and shaped to work together to assist with the positioning of proned patients to aid even distribution pressure reducing the number of pressure points and enable positioning in the neutral position to reduce the need for frequent repositioning and therefore need for trained manpower, which in significant shortage due to the surge in COVID patients on 'Critical Care.'
Length of time use the device has been in use.	Device has been in use since January 2021

### 3. ABBREVIATIONS

AE	Adverse event
ADE	Adverse Device Effect
CI	Chief Investigator
CRF	Case Report Form
CRO	Contract Research Organisation
CT	Clinical Trials
CTA	Clinical Trials Authorisation
GCP	Good Clinical Practice
GP	General Practitioner
ICF	Informed Consent Form
ICH	International Conference of Harmonisation
LUHFT	Liverpool University Hospitals NHS Foundation Trust
MHRA	Medicines and Healthcare products Regulatory Agency
NHS	National Health Service
NRES	National Research Ethics Service (previously known as COREC)
PI	Principal Investigator
PIL	Participant/ Patient Information Leaflet
R&I	R&I Department
REC	Research Ethics Committee
SAE	Serious Adverse Event
SADE	Serious Adverse Device Effect
SIL	Subject Information Leaflet (see PIL)
SOP	Standard Operating Procedure
TMF	Trial Master File
USADE	Unanticipated Serious Adverse Device Effect

#### **4. BACKGROUND AND RATIONALE**

During the COVID-19 pandemic, intensive care units (ICUs) across the country have been inundated with increasing numbers of COVID patients. Hypoxic patients in ICU require mechanical ventilation and this can be improved by proning these patients to improve oxygenation and prevent ventilator-induced lung injury (Guerin et al, 2013). Standard practice is to use standard hospital pillows to support the pelvis and chest of the patient while they are proned. These pillows do not provide much support to the patients and often need to be adjusted due to the patient 'sinking' into them. Prolonged pronation also leads to pressure sores in these anatomical locations which burden the Trust financially and also cause distress to patients.

A new proning pillow system was developed by [name] and manufactured for the ICU in Aintree hospital which is made from polyurethane memory foam designed to relieve pressure on the patients and prevent pressure sores that often occur during prolonged proning. The pillow system is also designed to withstand the load of heavier patients and reduce the risk of 'sinking' into the pillows when proned for long periods of time.

The aim of the study is to compare the performance of the new proning pillow system with standard pillows, particularly in relation to the risk of pressure sores, by evaluating differences in chest and pelvis interface pressures between the two pillow types. This will be done by having healthy NHS staff lie on the pillows in the prone position for a short period of time while recording the pressure distribution on the pillows using pressure mats placed between them and the pillows. This will help understand the relative risk of pressure sores developing when the new pillow system is used. It is hypothesised that the new pillow system does not increase the risk of pressure sores developing.

The new proning pillow system is a Class 1 CE marked medical device. The proning pillow system consists of a chest pillow and a pelvis pillow made from memory foam designed to reduce contact pressures and peak interface pressures in patients and allow patients to be placed in neutral position for ventilation.

This research is to be submitted in fulfilment of an academic qualification, a Masters of Science in Clinical Sciences (Clinical Engineering). The student will be doing this project under supervision. The student will recruit participants, take informed consent and take measurements.

## 5. OBJECTIVES

### 5.1 Primary Objective

To evaluate any differences in chest and pelvis interface pressures between novel proning pillows and standard pillows used in ICU.

### 5.2 Secondary Objectives

None

## 6. CROSS-SECTIONAL COMPARATIVE DESIGN

### 6.1 Summary of Study Design

Each participant will use both the Proning Pillow System and standard pillows. Each participant will only visit once with no further follow-up periods.

### 6.2 Primary and Secondary Endpoints/Outcome Measures

The primary outcome measure is the peak interface pressure, as measured by the pressure mat, for both types of pillows.

### 6.3 Study Participants

#### 6.3.1 Overall Description of Study Participants

Healthy participants working for the NHS.

#### 6.3.2 Inclusion Criteria

- Work for Liverpool University Hospital NHS Foundation Trust
- Participant is willing and able to give informed consent for participation in the study.
- Agree to have weight, height, chest and waist measurements taken
- Agree to the study protocol
- Aged 18 years or above.

#### 6.3.3 Exclusion Criteria

The participant may not enter the study if ANY of the following apply:

- Presentation of skin lesions
- Absence of any limb
- Female participant who is pregnant

- Have a lower back problem
- Pain or injury in shoulders or arms
- History of conditions that would make it difficult to lie prone, such as pressure injury or surgery within six months leading up to the study
- Any conditions that significantly affect movement and sensation such as diabetes or mobility limitations

## 6.4 Study Procedures

### 6.4.1 Screening and Eligibility Assessment

Staff from the Clinical Engineering Department at the Royal Liverpool University Hospital as well as staff from other departments such as the ICU in Aintree Hospital will be sent an email regarding the study and asked to participate. Staff must be over 18 years of age, and must agree to have their height, weight, chest and waist measured. The email will consist of a description of what the study is about. Interested participants will then be asked if they have any conditions mentioned in the exclusion criteria (Section 0). If they do, they will be excluded.

### 6.4.2 Informed Consent

The participant must personally sign and date the latest approved version of the informed consent form before any study specific procedures are performed.

Written and verbal versions of the participant information and Informed consent will be presented to the participants detailing no less than: the exact nature of the study; the implications and constraints of the protocol; the known side effects and any risks involved in taking part. It will be clearly stated that the participant is free to withdraw from the study at any time for any reason without prejudice to future care, and with no obligation to give the reason for withdrawal.

The participant will be allowed as much time as wished to consider the information, and the opportunity to question the Investigator, their GP or other independent parties to decide whether they will participate in the study. Written Informed Consent will then be obtained by means of participant dated signature and dated signature of the person who presented and obtained the informed consent. The person who obtained the consent must be suitably qualified and experienced, and have been authorised to do so by the Chief/Principal Investigator. A copy of the signed Informed Consent will be given to the participants if requested. The original signed

form will be retained at the study site.

#### **6.4.3 Baseline Assessments**

Height, weight, gender.

#### **6.4.4 Randomisation and Codebreaking**

All participants will lie on both sets of pillows. The only randomisation will be the order of pillows that participants will be asked to lie on.

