#### **6.4.5 Subsequent assessments**

Once informed consent has been taken, each participant will have their height, weight, waist and chest size measured and recorded, along with their gender. Participants will be asked to remove any belts or large objects that may interfere with the study. The following will then be repeated 3 times for each set of pillows: Each participant will be given instructions and be asked to lie down on the pillows (adjusting the position of the pillows to suit their height if necessary). The participant will then be given a short period of time (~1 minute) to get comfortable. The pressure mat data recording will then start, and the co-investigator will press down on the pressure mat at the approximate location of anatomical landmarks. The participant will continue to lie on the pillow for approximately 3 further minutes to allow pressure measurements to be taken. The participant will be asked to stand up and will be given a short rest period (~30 seconds) before being asked to reposition themselves back on the pillows and get comfortable.

Following this the participant will be given a period of time to recover while the pillows are changed to either standard hospital pillows or the novel proning pillows (the order will be randomized). They will then be asked to lie down again, get comfortable and have pressure measurements taken in the same way as before.

No follow-up assessments will take place.

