## **19.2 Description of Statistical Methods**

Suggested statistical approach in more detail.

A model-based approach to hypothesis testing will be applied. This allows incorporation of complexities such as repeated measurements, nested classification factors, unbalanced observations, and determination of the magnitude of effects [Harrell]. The chosen model belongs to the family of linear mixed-effects models [Pinheiro], and it is formulated as follows:

$$\mathbf{y}_{ij} = \mathbf{X}_{ij}\boldsymbol{\beta} + \mathbf{Z}_{i,j}\mathbf{b}_i + \mathbf{Z}_{ij}b_{ij} + \epsilon_{ij}, \quad i = 1, \dots, M, \quad j = 1, 2$$

$$\mathbf{b}_i \sim N(0, \boldsymbol{\Psi}_1), \quad b_{ij} \sim N(0, \sigma_2^2), \quad \epsilon_{ij} \sim N(0, \sigma^2 \mathbf{I})$$

where  $\mathbf{y}_{ij}$  is the measured peak pressures for subject  $i$  from a sample of size  $M$ , at anatomic location  $j$  (corresponding to chest and pelvis.) The fixed-effects treatment contrast matrices  $\mathbf{X}_{ij}$  encode the experimental factor pillow type (new versus standard).  $\mathbf{Z}_{i,j}$  represents the design matrices of the level-1 random effects for subject  $i$  on the measurements for anatomic location  $j$  within subject  $i$ .  $\mathbf{Z}_{ij}$  represents the design matrices of the level-2 random effects for anatomic location  $j$  within subject  $i$ . The normally distributed  $\mathbf{b}_i$  are assumed to be independent for different  $i$ ; and the normally distributed  $b_{ij}$  are assumed to be independent for different  $i$  or  $j$  and to be independent from  $\mathbf{b}_i$ ; finally, the within-group errors  $\epsilon_{ij}$  (which represent all the variability which is not explained by the model) are assumed to be independent for different  $i$  or  $j$  and to be independent from the random effects. The parameters to be estimated by the above model are represented by the 2-vector  $\boldsymbol{\beta}$ , the variance  $\sigma_2^2$ , and the entries of the 2x2 matrix  $\boldsymbol{\Psi}_1$  (it should be noted that since the latter is a covariance matrix which is forced to be positive definite by construction, only 2 entries need to be estimated.) The total number of parameters is therefore 5.

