### 19.2.1 The Number of Participants

Due to the lack of available information in published sources to determine the effect sizes required for sample size calculation, and due to the complexity of the experimental design, no formal power analysis is possible.

However, a heuristic approach will be applied [Harrell] based on the complexity of the model used to test the experimental hypotheses, namely that the sample size should be of the order of 10 times the number of parameters estimated by the model. With the previous definition of the model complexity, we estimate the sample size to be of the order of  $M = 50$ .

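### Pillow order is randomised, but the model has no period term and no balance of order is stated, so a first-to-second shift would distort the standard error of the pillow effect.

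*Combined protocol and SAP*

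**What the plan says.** Section 6.1: "Each participant will use both the Proning Pillow System and standard pillows". Section 6.4.4 adds: "The only randomisation will be the order of pillows that participants will be asked to lie on". Under section 6.4.5 all three repeats on one set are finished before the change to the other, so there are two periods. No section states an allocation ratio, blocking or an order list.

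In section 19.2 the fixed-effects matrices "encode the experimental factor pillow type (new versus standard"). The fixed-effect vector has two entries, and section 19.2.2 names the second as the pillow difference. The other parameters are one variance, "and the entries of the 2x2 matrix" Psi_1, of which two are said to need estimating. Hence "The total number of parameters is therefore 5". Neither this model nor the summary in section 9.1 mentions period or order.

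On size, section 19.2.1 says that "no formal power analysis is possible" and uses a rule that "the sample size should be of the order of 10 times the number of parameters estimated by the model". Testing is at 0.01, and approximate confidence intervals will be reported (sections 9.3 and 19.2.2).

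**The concern.** The analysis does not use what was randomised. Peak pressure may differ between the first and second set for reasons unrelated to the pillow, such as getting used to the prone position or tiring. That shift enters the new-minus-standard difference with one sign in participants who start on the new set and the opposite sign in those who start on the standard set. Averaging the three repeats does not reduce it, because all three fall in the same period.

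The standard error of the pillow effect is then wrong in one direction or the other. The plan itself calls the sample small and tests at a strict level. Its background section hypothesises no increase in pressure-sore risk, so the width of the interval matters even where power is high.

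**Working it through.** **Plan's own figure.** 2 fixed effects + 1 variance + 2 entries of Psi_1 = 5, and 10 x 5 = 50. The sample size reproduces.

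**Inputs.** From the documents: n = 50, alpha = 0.01 (taken as two-sided, since the null is no difference), and both sets used by everyone in random order. Assumed, because the documents give no values: true pillow effect d and full first-to-second shift p, both in SDs of the within-participant difference. The shift is additive, common to all participants, and without carry-over. Each participant contributes one paired difference.

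**Case A: Psi_1 includes a random pillow effect.** The difference is D_i = d + s_i p + e_i, with s_i = +1 or -1 by order and e_i of variance 1. Without a period term its variance is about 1 + p^2, so the reported SE is multiplied by sqrt(1 + p^2). Power is the upper tail of a noncentral t with 49 df, noncentrality d sqrt(50)/sqrt(1 + p^2) and critical value 2.680. Results for d = 0.5:

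| Shift p | SE multiplier | Power without period term |
|---|---|---|
| 0 | 1.000 | 0.80 |
| 0.2 | 1.020 | 0.78 |
| 0.3 | 1.044 | 0.76 |
| 0.5 | 1.118 | 0.68 |
| 0.75 | 1.250 | 0.56 |

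With a period term (48 df), power is about 0.80 at 25/25 and about 0.79 under coin-flip order, whatever the shift. Simulation of 200,000 trials per setting agrees with the table under coin-flip order.

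Other effect sizes, coin-flip order, p = 0.5, without v with the term:
- d = 0.3: 0.23 v 0.29
- d = 0.7: 0.956 v 0.984
- d = 0.8: 0.990 v 0.998

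At p = 0.75 and d = 0.7 it is 0.895 v about 0.984.

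Balance alone does not cure this. At 25/25 with p = 0.5 and d = 0.5, power without the term is 0.70. There the shift cancels from the estimate but not from the reported SE. The 99% interval is 2%, 12% or 25% wider than with the term at p = 0.2, 0.5 or 0.75, and the test is conservative (type I error 0.009, 0.004 and 0.001).

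An unbalanced split also moves the estimate in that trial by (n1 - n2)/50 of the shift. At 30:20 this is 10/50 = 0.2 of it. A split of 30:20 or worse has probability 0.20 under coin-flip order.

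**Case B: Psi_1 has no random pillow effect.** Take independent repeats with SD 1, an intercept per participant and location, coin-flip order and a shift of 0.5 replicate SD.
- *Two locations, three repeats (6 readings per pillow).* True variance of a participant's mean difference: 2/6 + 0.25 = 0.583. The shift adds 12 x 0.25^2 = 0.75 to about 10 residual df per participant, so the fitted residual variance is about 1.075 and the variance used is 1.075 x 2/6 = 0.358. The ratio is 1.63, with square root 1.28. The critical value 2.586 acts like 2.586/1.28 = 2.03, so type I error is about 0.04.
- *One location (3 readings per pillow).* True 2/3 + 0.25 = 0.917, used 1.075 x 2/3 = 0.717. The ratio is 1.28, with square root 1.13. The critical value 2.596 acts like 2.30, so type I error is about 0.02.

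Simulations of these simplified set-ups gave about 0.04 and 0.02.

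**Cost of the term with no shift.** At 25/25 the 99% interval is 0.1% wider. Under coin-flip order, power goes from 0.80 to 0.79 at d = 0.5. The variance factor is 1.0213, so the term gains only when p exceeds sqrt(0.0213) = 0.146.

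**The case against.** The strongest reply is that nothing in the documents shows a shift. The procedure works against one: about a minute to settle before recording, a short rest between repeats, and "a period of time to recover while the pillows are changed". At 0.2 SD the gain is 1 to 2 power points, and under coin-flip order it is nil below about 0.15 SD. The 10-point loss needs a shift of 0.5 SD with an effect near 0.5 SD; at d = 0.7 the loss at that shift is about 3 points. The plan claims no power, so no stated operating characteristic fails. Period could be added later as a justified deviation under section 9.6. All of this stands, and it limits the severity. It does not remove the case for prespecifying: a later term is chosen with the data in view, and it needs an order record that section 6.7 does not list among the CRF source items.

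A reader might go further and infer that the pillow effect is biased. It is not, over the randomisation; only a single unbalanced trial is displaced, in proportion to its imbalance. A reader might also infer that only precision is at stake. The documents do not support that either, because section 19.2 does not say what the two dimensions of Psi_1 are.

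**Conclusion.** The point holds as a cheap improvement of low to moderate severity. The stated model leaves any common period shift in the pillow difference. With a random pillow effect this costs power and interval width: about 10 to 12 points at d = 0.5 and a shift of 0.5 SD, 1 to 2 points at 0.2 SD, and little when d is 0.7 or more unless the shift is large. Without a random pillow effect, type I error under coin-flip order could be roughly 0.02 to 0.04 instead of 0.01, at a shift of half the replicate SD. All sizes rest on assumed shifts, SDs and effects, an additive shift and no carry-over.

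It might also be inferred that one more parameter makes the count 6 and the required sample 60. The documents do not support this. The count of 5 itself needs checking: it omits the residual variance that the model defines, and an unrestricted 2x2 covariance matrix has three distinct entries, not two. The rule is also stated only as an order of magnitude.

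**What to change.** - **Section 19.2:** add one fixed effect for period (first or second pillow set), and state what the two dimensions of Psi_1 are.
- **Sections 6.4.5 and 6.7:** state that each participant's pillow order is recorded.
- **Section 6.4.4:** allocate order in blocks aiming at 25/25, for example five blocks of 10.
- **Sections 9.2, 19.2 and 19.2.1:** say that period adds one parameter to whatever count 19.2 gives once that count is checked. Keep 50 as the order of magnitude from the heuristic, with no change in enrolment.

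The cost is wording, an order list and one degree of freedom. If there is no shift, the term loses about one power point under coin-flip order and essentially nothing at 25/25.

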#### **6.4.5 Subsequent assessments**

Once informed consent has been taken, each participant will have their height, weight, waist and chest size measured and recorded, along with their gender. Participants will be asked to remove any belts or large objects that may interfere with the study. The following will then be repeated 3 times for each set of pillows: Each participant will be given instructions and be asked to lie down on the pillows (adjusting the position of the pillows to suit their height if necessary). The participant will then be given a short period of time (~1 minute) to get comfortable. The pressure mat data recording will then start, and the co-investigator will press down on the pressure mat at the approximate location of anatomical landmarks. The participant will continue to lie on the pillow for approximately 3 further minutes to allow pressure measurements to be taken. The participant will be asked to stand up and will be given a short rest period (~30 seconds) before being asked to reposition themselves back on the pillows and get comfortable.

Following this the participant will be given a period of time to recover while the pillows are changed to either standard hospital pillows or the novel proning pillows (the order will be randomized). They will then be asked to lie down again, get comfortable and have pressure measurements taken in the same way as before.

No follow-up assessments will take place.

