**Chest pillow**

**Pelvic pillow**

In each case, a pressure mat (BodiTrak Pro standard, CE 0413) will be placed on each pillow (chest and pelvis). The participant will lie on top of the pillows. The pressure mat will be connected to a laptop which will capture the data using the BodiTrak Pro software.

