## **9. STATISTICS**

### **9.1 Description of Statistical Methods**

A model-based approach will be used to test the hypothesis. This approach considers complexities such as repeated measurements, unbalanced observations and determination of the magnitude of effects. The model incorporates the measured peak pressure for each participant at each anatomic location (chest and pelvis) and the two different pillow systems (new and standard).

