### **9.4 Procedure for Accounting for Missing, Unused, and Spurious Data.**

The chosen statistical methods can be applied even with unbalanced observations (i.e. outcomes need not be observed for all possible combinations of the experimental factors pillow and position) [Pinheiro]. Due to the nature of the experimental design and the type of

measurements involved, no missing, unused, or spurious data are expected.

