#### **19.2.3 Procedure for Accounting for Missing, Unused, and Spurious Data.**

The chosen statistical methods can be applied even with unbalanced observations (i.e. outcomes need not be observed for all possible combinations of the experimental factors pillow and position) [Pinheiro]. Due to the nature of the experimental design and the type of measurements involved, no missing, unused, or spurious data are expected.

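### Could the investigator's landmark presses, made while the mat is recording, end up as the primary-endpoint peak?

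*Combined protocol and SAP*

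**What the plan says.** Section 6.4.5 sets the order of events for each repeat. The participant lies down and has about a minute to settle. Then: "The pressure mat data recording will then start, and the co-investigator will press down on the pressure mat". These presses are aimed at anatomical landmarks. The next sentence reads: "The participant will continue to lie on the pillow for approximately 3 further minutes to allow pressure measurements to be taken". The cycle is done three times on each pillow set.

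Section 6.2 defines the endpoint: "The primary outcome measure is the peak interface pressure, as measured by the pressure mat, for both types of pillows". The Synopsis adds that the mat lies between the participant and the pillow, and section 7.1 puts a mat on both the chest and the pelvis pillow.

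On the analysis side, section 9.1 says "The model incorporates the measured peak pressure for each participant at each anatomic location", and section 19.2 uses the same response variable. Neither describes how a peak is extracted from a recording. Section 9.4, on missing and spurious data, says that "no missing, unused, or spurious data are expected", and section 19.2.3 repeats this.

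**The concern.** A peak is a maximum, so one brief outside load can replace it entirely. Further minutes of clean recording do not dilute it. Recording begins before the press, and no section states a time window, a sensor region or a rule for dropping frames. An analyst who took the maximum of the whole file would break no written rule.

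Peak pressure is the only endpoint, and the pillow difference is the only primary comparison. Presses that read alike on both pillows would shrink that difference toward zero. The background section hypothesises that the new system is no worse for pressure-sore risk, so shrinkage would favour the study's own expectation. Presses that read differently on the two pillows could create a difference where there is none. This is conceivable because the pillows differ in material and thickness and the press is not standardised. The statement that no spurious data are expected also sits oddly beside a procedure that puts investigator-made pressure into every recording.

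**Working it through.** **Exposure (from the documents).**
- Participants: 50 (section 9.2). The plan's own derivation reproduces: 10 x 5 parameters = 50 (sections 19.2 and 19.2.1). The concern does not depend on it.
- Recordings: 50 participants x 2 pillow sets x 3 repeats = 300, each with presses (section 6.4.5).
- Peaks: 300 x 2 sites = 600 at most. Section 6.4.5 does not say how many landmarks are pressed or whether both mats are pressed every time.
- Lying time after the presses: 6 recordings x about 3 minutes = about 18 minutes per participant.

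**What a whole-recording maximum would do.** Let S and N be the participant's own peaks on the standard and new pillows, and P a press of equal size on both. If press and body load do not interact, the recorded difference is max(S, P) - max(N, P). The documents give none of these pressures. With assumed S = 100 and N = 80 (true difference 20):

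| Assumed P | Recorded difference | Loss |
|---|---|---|
| 70 | 100 - 80 = 20 | 0% |
| 85 | 100 - 85 = 15 | 25% |
| 90 | 100 - 90 = 10 | 50% |
| 95 | 100 - 95 = 5 | 75% |
| 100 or more | P - P = 0 | 100% |

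The range is 0% to 100%. That is the logical span of the formula and not an estimate for this trial.

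**A simulation gives the same picture, again on assumed values only.** Settings: 50 participants, 3 repeats per pillow, one site, a paired t test on participant means at two-sided 0.01 in place of the mixed model, standard-pillow peak 60 mmHg, true difference (new minus standard) -10, between-participant SD 12, within-participant SD 6, press SD 15.

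| Mean press (mmHg) | Peaks that are the press | Mean estimate | Power |
|---|---|---|---|
| Presses excluded | 0% | -10.0 | about 100% |
| 30 | 11% | -8.9 | about 100% |
| 50 | 40% | -6.0 | 99% |
| 70 | 77% | -2.3 | 15% |
| 100 | 99% | -0.2 | 1% |

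With no true difference and equal presses, the rejection rate stays at about 1%. If presses read 10 mmHg higher on the new pillow, mean presses of 50, 70 and 100 mmHg give false differences of 4.0, 7.7 and 9.9 mmHg, with rejection in 86% to over 99% of trials. All of this applies only if press frames enter the peak.

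**Do the documents put press frames into the peak?**
1. *Sequence.* Section 6.4.5 has settling, start of recording, presses, then a further period whose stated purpose is measurement. The presses therefore come before the measuring.
2. *Endpoint.* Section 6.2 names interface pressure, and the Synopsis locates it between participant and pillow. A hand pressing on the mat is not that quantity.
3. *Use of the presses.* No purpose is stated, but pressing at anatomical landmarks most plausibly marks their position on the pressure map. Such marks work only if someone finds the press frames, and that person then knows which frames to leave out.
4. *Sections 9.4 and 19.2.3.* These concern unbalanced observations across pillow and position. Their remark on spurious data is a forecast and does not direct anyone to keep press frames.

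No passage calls for press frames to be analysed, and items 1 and 2 point the other way.

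**The case for a change.** The strongest case for a change is that implication is not a rule. The sentence about 3 further minutes says how long the participant lies there. It does not say that the peak comes only from that time. Someone unfamiliar with the study could process the whole file, and someone who crops it would choose the start and length with the data in view. A sentence would cost little and protect the only endpoint.

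Part of this stands. The presses do fall inside the recording, and the extraction rule is not written down. But the harm needs an analyst to treat a deliberate press, made by the study team at a known early point in every recording, as the participant's own interface pressure. The freedom in choosing the crop is narrow: the natural start is after the last press, and the same period of about 3 minutes follows on both pillows.

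The more elaborate remedies gain nothing clear. A fixed 2-minute window has no basis in the documents and would use 6 x 2 = 12 of the roughly 18 post-press minutes, discarding about 6 that contain no press. A separate landmark recording adds a step to every repeat to remove frames that can simply be cropped.

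**Conclusion.** No change to the plan is called for. The observation is accurate: recording starts before the presses, and no section says in terms which part supplies the peak. Section 6.4.5 nevertheless places measurement after the presses, and section 6.2 with the Synopsis defines a quantity that a hand press is not. What remains is an extraction detail that analysts would fill sensibly by taking the peak after the last press, over the same duration on both pillows.

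No size of effect can be claimed. Up to 600 peaks come from recordings that contain presses, but the number altered would be zero under the natural reading. Under the contrary reading the loss runs from 0% to 100%, set entirely by assumed pressures. The conclusion assumes that the analyst can recognise the press frames, which is reasonable because the study team makes the presses itself at a set point in each recording. It would need another look only if the final report showed peaks taken over whole recordings, presses included.
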